In general, the specific type of alcoholic beverage type consumed appears to be less important than the consistency with which alcohol is consumed. The beverage most likely to be inversely related to CHD in a given population tends to be the one most widely consumed in that population.^{10,21} Two systematic reviews of this topic have concluded that beverage type is relatively unimportant,^{22,23} while a recent meta-analysis found similar benefits from beer and wine but not spirits.²⁴ The effect of alcohol on high density lipoprotein-cholesterol (HDL-C; its major putative mediator) also does not differ by beverage type in short-term controlled experiments.²⁵ Thus, observational evidence generally supports the hypothesis that it is ethanol intake, *per se*, that is associated with lower risk of CHD. This also concurs with how alcohol intake is viewed by NIAAA and other bodies: a limit on total intake without differentiation by beverage type.

Although less well-studied, evidence overall suggests that other coronary outcomes commonly used in clinical trials (e.g., unstable angina, coronary revascularization) demonstrate similar associations with alcohol as does MI. Indeed, several cohort studies have shown similar relationships across all coronary outcomes.^{11,14,26-28}

Other vascular outcomes have also been studied extensively in relation to moderate drinking. The association of alcohol consumption with total stroke is complex, given differing associations with the major stroke types of ischemic and hemorrhagic stroke. Further, subtypes within these major stroke types may differ in their associations with alcohol, presumably due to disparate underlying etiologies.²⁹ Nonetheless, light-moderate drinking has been associated with a lower risk of ischemic stroke of approximately the same magnitude as for CHD, while hemorrhagic stroke appears to have a dose-dependent positive association with alcohol intake.³⁰ Etiologically, both effects could reflect an antiplatelet effect of alcohol.³¹

The relationship of moderate drinking with blood pressure, an important risk factor for CHD and all forms of stroke, is complex and not entirely consistent even in the hours following consumption.³² Sex-specific meta-analysis suggests a J-shaped association between alcohol and risk of hypertension among women but a roughly dose-response positive association among men; in neither sex was moderate drinking associated with significantly higher risk.³³

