There are numerous risk factors for CVD and diabetes, and these will be measured at baseline and at subsequent visits, including age, body mass index, hemoglobin, blood pressure, gender, race/ethnicity, healthy lifestyle, and other co-morbidities. Although randomization ensures that, on average, treatment groups will be balanced with respect to all of these factors, this may not be true in the given trial. Thus, we will assess the success of randomization by first comparing the baseline characteristics of participants in the treatment groups, and then re-assess treatment effects in secondary analysis after adjusting for the risk factors associated with the strongest imbalances. To adjust as finely as possible for confounding by measured risk factors, an additional secondary analysis will be conducted that adjusts for all measured risk factors.

Non-adherence to the assigned treatment is another potential challenge to power an unbiased treatment effect estimation that we will address in secondary sensitivity analysis by conducting *per protocol* and *as treated* analyses,⁸ by using instrumental variables methods,^{9,10} by potential outcomes

approaches,¹¹ by comparing the compliance estimates and by computing log rank tests weighted by time-varying probability of adherence.¹² *Per protocol* analysis excludes non-compliant participants from their respective arms. *As treated* analysis ignores treatment assignment but, rather, analyzes participants according to the amount of alcohol intake reported, regardless of what was assigned. The “contamination-adjusted intention-to-treat” uses instrumental variable analysis to address non-adherence in a two-stage approach. The potential outcomes approach is an estimation procedure for the intention-to-treat effect that maintains randomization-based properties under more plausible, non-ignorable noncompliance and non-ignorable missing-outcome conditions. The log rank tests weighted by time-varying probability of adherence involves modeling the probability of non-adherence given available covariate data, and then uses the inverse of these estimated probabilities, suitably stabilized, to reweight the log rank test statistic to mimic the study population that would have been observed, had there been no non-adherence

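### Section 8.1.1 chooses adjustment covariates by observed baseline imbalance, and does not limit its fully adjusted analysis to baseline values

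*Combined protocol and SAP*

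**What the plan says.** The primary analysis in section 8.1.1 is a site-stratified log-rank test for clustered data, with a Cox model adjusted for clinical site only. The diabetes outcome is to be analyzed in the same way.

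The next paragraph turns to risk factors. It says "these will be measured at baseline and at subsequent visits" and gives an open list, "including age, body mass index, hemoglobin, blood pressure, gender, race/ethnicity, healthy lifestyle, and other co-morbidities". It then sets out two secondary analyses:

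- **By imbalance.** The success of randomization is judged by "first comparing the baseline characteristics of participants in the treatment groups". The plan will then estimate the treatment effect again "after adjusting for the risk factors associated with the strongest imbalances". It gives no metric, threshold, number of covariates or candidate list.
- **Full adjustment.** To control confounding, "an additional secondary analysis will be conducted that adjusts for all measured risk factors". The time point of those measurements is not stated.

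HDL-C is not named in this paragraph. Section 1.2.2 describes it as alcohol's likely main mediator ("HDL-C; its major putative mediator"), while section 8.2 leaves its place in the mechanism open.

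**The concern.** Differences between randomized groups at baseline arise by chance, and their size says nothing about whether a variable predicts the outcome. Ranking covariates by imbalance can therefore bring in irrelevant variables and leave out age or prior CVD. The choice is made after the baseline data by arm are seen. With no rule for how many covariates or which measure of imbalance, two analysts could follow the text and report different adjusted hazard ratios.

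The full adjustment raises a different problem. The word baseline appears where the groups are compared, but not where the full adjustment is defined. Blood pressure and body mass index are on the list and can be updated at follow-up (Table 6.1 has blood pressure and weight at annual visits). Section 1.4.1 says that alcohol may move blood pressure either way and may add weight. Conditioning on such values removes or reverses part of the effect being estimated. A result presented as control of confounding could then be read as evidence about whether the primary finding was confounded.

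**Working it through.** **1. Reproduce the design anchor.** The plan attaches no figure to the adjusted analyses, so the primary design serves as reference. Inputs from section 8.2: abstention rate 0.026 per person-year, effective HR 0.838, 1% annual loss, 3,900 per arm, two-sided 0.05. From section 11.4: follow-up 4.5 to 7.5 years, mean 6.

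- Effective HR: 1 − 0.18 × 0.90 = 0.838.
- Events needed (Schoenfeld): 4 × (1.960 + 0.842)² / (ln 0.838)² = 1,006 after rounding up, with ln 0.838 = −0.1767.
- Events expected, with exponential rates 0.026 and 0.026 × 0.838, 1% loss and uniform 3-year accrual: 1,009.
- Power: Φ(√1009/2 × 0.1767 − 1.960) = Φ(0.85) = 80%.

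The plan's 7,800 and 80% reproduce.

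**2. What choosing by imbalance does.** The paragraph names eight items or groups. With eight independent covariates and an assumed 5% screen, the probability of at least one flagged imbalance by luck is 1 − 0.95⁸ = 34%.

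An illustrative simulation under no treatment effect used a linear outcome, 500 per arm, eight covariates with coefficients 0.4, 0.3, 0.2, 0.1 and four zeros, and 4,000 repeats. It compared adjustment for the two most imbalanced covariates with adjustment for the two strongest prognostic ones.

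| Adjustment | Type I error | Mean model SE | Empirical SE |
|---|---|---|---|
| None | 0.051 | 0.072 | 0.073 |
| Two most imbalanced | 0.040 | 0.070 | 0.067 |
| Two pre-specified prognostic | 0.051 | 0.065 | 0.065 |
| All eight | 0.051 | 0.063 | 0.064 |

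The imbalance rule picked the two strongest predictors 3.7% of the time; pure chance is 1/28 = 3.6%. It is slightly conservative, and its model standard error is larger than the actual spread of the estimates. It gives up precision but creates no false positives.

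**3. What prognostic baseline adjustment could gain in a Cox model.** In 300 simulated trials per setting (n = 7,800, 2.6% per year, HR 0.838 taken as conditional on the covariates), unadjusted and adjusted power were 78.7% and 80.8%, 74.6% and 78.5%, and 69.2% and 76.7%, for assumed log-hazard SDs of 0.6, 0.8 and 1.0. The gains are 2.1, 3.9 and 7.5 points; repeat runs gave about 2 to 3, 3 to 4 and 6 to 8. The prognostic SDs are assumptions. Unadjusted power is below 80% because 0.838 was set as the conditional HR, so these are differences between analyses and not corrections to the plan's power.

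**4. What adjusting for follow-up values could do, if they were used.** Let m be the net share of the log-HR carried by the adjusted variables, positive for benefit and negative for harm. Then adjusted HR = 0.838^(1−m), and power is Φ(√1009/2 × |ln HR| − 1.960), with events held at 1,009. The documents give no value for m.

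| Assumed m | Adjusted HR | Power |
|---|---|---|
| −25% | 0.802 | 94% |
| −10% | 0.823 | 87% |
| 0 | 0.838 | 80% |
| 10% | 0.853 | 71% |
| 25% | 0.876 | 56% |
| 50% | 0.915 | 29% |

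A path through weight gain or raised blood pressure would give negative m; a protective path through HDL-C would give positive m. The rows with negative m are no advantage: they overstate the effect of assignment.

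**5. Can all measured risk factors be implemented?** Diet and physical activity, the natural content of a healthy-lifestyle covariate, come from optional questionnaires (section 6.1.1.3), and no rule is given for those without them. The list includes hemoglobin, but Table 6.1 and section 6.2.1.1 name no hemoglobin measure other than HbA1c. If HbA1c is meant, follow-up values in the diabetes model would condition on a measurement that can define the outcome (section 3.5.2).

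**The case against.** A reader might infer that the plan will put follow-up values, HDL-C among them, into the treatment-effect model and so pull the result towards the null. The documents do not support that. The sentence on later visits describes data collection. The rationale is chance imbalance and confounding, both baseline ideas in a randomized comparison; several listed items (age, gender, race/ethnicity) are fixed traits; and the only comparison described is of baseline characteristics. HDL-C is not on the list, although the list is open and section 8.1.2 treats HDL-C as a CVD risk factor. Nor is the direction general: weight or blood pressure paths could carry harm, and adjusting for them would move a protective hazard ratio away from the null.

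It can also be said that, on the baseline reading, the full adjustment already contains the prognostic factors whose precision the imbalance rule gives up; that a fixed imbalance rule does not inflate type I error; and that both analyses are secondary. All of this stands, and it limits the weight of the point.

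It does not remove it. The imbalance rule is stated and a better method is available from data already collected. The full adjustment has no defined covariate set, no time point and no handling of optional data. The plan would also yield two adjusted hazard ratios without saying which one takes precedence.

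**Conclusion.** The point holds as a change that should be made to the secondary analyses. Selection by observed imbalance is a stated rule that ignores prognosis and leaves the choice of covariates open after baseline data are seen. Its cost is precision and reproducibility, not false positives. The full adjustment is ambiguous: baseline is the likely intent, but the text does not exclude post-randomization values.

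The primary log-rank test, its power and the site-adjusted Cox hazard ratio are not affected. The power gains rest on assumed prognostic strength. The altered hazard ratios rest on two assumptions together: that follow-up values are used, and the assumed share and sign of the paths adjusted for. None of these figures is a prediction for this trial.

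**What to change.** Replace both sentences in section 8.1.1 with one pre-specified adjusted Cox model for each of the primary and diabetes outcomes:

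- Keep the site terms and the allowance for household clustering.
- Use baseline values of prognostic factors collected on all participants, for example age, sex, clinical CVD, smoking, systolic blood pressure, and total and HDL cholesterol. Add baseline diabetes for the primary outcome only, since the diabetes analysis excludes those who have it. Leave out items from optional questionnaires and findings available only from existing medical records.
- State coding and the handling of missing baseline values.
- State that no post-randomization measurement enters a treatment-effect model outside an analysis labelled as mediation.
- Report baseline imbalance descriptively only.

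The list should be fixed before any comparison by arm is seen. The cost is SAP wording; no new data, visits or participants are needed.

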events. If anything, the uncertainty related to the health effects of alcohol consumption is even larger, and hence confidence in applying its short-term effects to longer-term chronic disease outcomes is necessarily lower. Moreover, epidemiological studies have identified potential harms from even moderate drinking. These too have not been confirmed in randomized trials, yet patients, physicians, and public health professionals are all asked to use far-from-definitive data in making recommendations. Only a randomized trial can provide conclusive evidence as to whether or not daily alcohol consumption lowers risk of cardiovascular disease or diabetes, while also collecting information on other outcomes that will allow for a more thorough and unbiased understanding of all potential effects of moderate alcohol consumption. As such, a definitive randomized trial of moderate alcohol consumption compared with abstention can play a crucial role in the eventual establishment of the first fully evidence-based guidelines for the use or nonuse of alcohol.

The rationale for a randomized trial of moderate alcohol consumption is further underscored by the inherently inconclusive nature of epidemiological evidence. For example, with regard to alcohol consumption, differences in the associations of alcohol consumption with risk of cardiovascular disease have been noted in different geographic regions.^{96,97} Some meta-analysts express concern about the possibility of inappropriate reference groups in many cohort studies and highlight the advantage of randomized trials with mortality endpoints.⁹⁸ In addition, observational studies using genetic variants as proxies or instruments for alcohol consumption have come to inconsistent conclusions.^{99,100}

Given the inability to judge causality in epidemiological studies and the limited scope of previous randomized trials of moderate alcohol consumption, equipoise exists about the health effects of moderate drinking. In conjunction with the urgent need to provide an evidence base for drinking guidelines worldwide, this uncertainty provides the rationale for a long-term, randomized trial of moderate drinking compared with no or very low alcohol intake on cardiovascular disease, diabetes, and mortality.

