5 INTERVENTION

5.1 INTERVENTION DESCRIPTION

The MACH15 Trial will include two intervention arms: one will assign participants to consume a moderate daily amount of alcohol defined as ~15 g (a standard U.S. serving) and the other will assign participants to abstain from alcohol. Because standard units of alcohol vary between countries, to ensure uniformity, clinical sites will convert ~15 g of alcohol to the standard unit for their localities. This comparison represents a clinical scenario in which a moderate amount of alcohol is ‘recommended’ by a clinician for potential health benefits. The intervention will average 6 years in duration, with a common participant close-out date. Although the beverage choice of participants will be actively and repeatedly monitored, participants in the alcohol arm can choose to consume beer, wine, or spirits. There is no clear evidence that any one beverage is preferable, and this approach both mimics usual drinking patterns and offers the greatest opportunity for long-term adherence.

The intensity of intervention will be similar in both arms of the trial, except for the assignment to consume or not consume alcoholic beverages. Promotion of adherence will be an important goal throughout the trial. Continuous feedback and discussions of challenges and solutions will take place between clinical site staff (e.g., health coach, dieticians), coordinators and participants. Adherence assessments will be performed during in-person visits, phone visits, and via individualized automated participant contacts (e.g., smart phone application, email, text messages) at varying frequencies throughout the trial (see Section 5.4.2). Participants in the alcohol arm will receive adherence counseling if they fall below 85% adherence (more than 4 non-adherent days per month) while those in the abstention arm will receive counseling if they fall below 100% adherence.

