5.2.2 ABSTENTION ARM

Participants in the abstinence arm will abstain from drinking alcohol for approximately 6 years. Complete abstinence is recommended to ensure sharp contrast between the two trial arms; however, a modest degree of tolerance towards alcohol consumption in the abstinence arm will be allowed. Participants may consume a limited number of alcoholic beverages at their discretion on special occasions. This will be monitored by site staff to ensure that adherence to the protocol is not compromised.

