7.4.4 REPORTING OF PREGNANCY

The use of alcohol is a known risk factor during pregnancy. One of the main inclusion criteria in the trial is postmenopausal status. Therefore, women included in the trial will have a postmenopausal status and pregnancies are not expected to occur. However, if a pregnancy does occur, participation will be discontinued on the intervention.

7.4.5 INCIDENT CONDITIONS THAT RESULT IN PERMANENT OR TEMPORARY STOPPING OF ALCOHOL BUT CONTINUED FOLLOW-UP FOR OUTCOMES

The use of alcohol may be harmful in the following conditions. For this reason, the intervention will be discontinued at least temporarily in the following incident conditions (this list is not intended to be exhaustive):

- Dementia
- Heart failure Class III or IV
- Breast cancer
- Gastric bypass surgery
- Serious chronic liver disease (e.g., active hepatitis B and C infections) or liver tests (aspartate aminotransferase [AST], alanine aminotransferase [ALT] and gamma-glutamyl transpeptidase [GGT]) >2 times the upper limit of the normal range using local standards; GI bleeding.
- Estimated glomerular filtration rate (eGFR) drops to <30 ml/min /1.73m² or end-stage renal disease (ESRD)
- Ongoing use of any medication for which alcohol consumption is contraindicated
- A Patient Health Questionnaire (PHQ-9) score ≥15 or a positive response on question 9 dealing with suicide ideation
- Any organ transplant
- Pregnancy
- Development of alcohol use disorder

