8.2 SAMPLE SIZE CALCULATIONS

Sample size calculations involved extensive explorations over a range of primary endpoint definitions and baseline rates, baseline adherence rates and improvements to these due to household network effects, proportions of households with 1, 2 and 3 eligible members, intra-household correlation coefficients, and minimum expected effect sizes.

We originally assumed that our trial will be individually randomized trial, and that the primary combined expanded CVD incidence endpoint in the abstention arm will have a rate of 0.026/person-year, modestly higher than the 2.2% annual rate observed in SPRINT,¹⁵ increased slightly because, unlike SPRINT, we are including diabetic individuals and total mortality as an outcome and excluding CHF alone. Participants will enroll during the first 3 years and then will be followed for an average of 6 years. We have assumed that there will be 1% annual loss to follow-up (LTF) in both groups, and 10% non-adherence at any point in time over follow-up for participants who are the sole person in their household to be randomized, leading, for these participants, to an effective hazard ratio of 0.838 under an assumed true hazard ratio of 0.82 as in Ronksley, et al.¹⁶ Under these assumptions, to provide a minimum of 80% power at a two-sided 0.05 significance level for detecting a 18% relative decrease in the intervention group endpoint rate, for an individually randomized trial design with one participant per household, we will need 3,900 participants per arm,¹⁷ for a total of 7,800.

Although we conservatively powered the trial for an expected relative risk (RR) of 0.82, there is substantial evidence suggesting that for CVD, an RR of 0.75 is likely to be observed. If so, we will have adequate power for baseline rates as low as approximately 0.0125/person-year, significantly lower than the observed rate in MESA.

[figure not shown]
TABLE 8.1: POWER FOR CARDIOVASCULAR DISEASE ANNUAL EVENT RATES

Annual Event Rate	Relative Risk		
	RR=0.82	RR=0.80	RR=0.75
1.4%	55%	65%	84%
1.8%	65%	75%	92%
2.2%	74%	83%	96%
2.6%	80%	88%	98%
3.0%	85%	92%	99%
3.4%	89%	94%	99%

Figure 8.1 presents power for different values of relative risks (0.80, 0.82 and 0.84) as a function of a range of plausible annual events rates (from 0.014/year to 0.035/year).

FIGURE 8.1: POWER FOR PRIMARY ENDPOINT

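### Alcohol stops ordered for illness under Section 7.4.5 have no handling rule in the as-treated and per-protocol analyses, which can then show a benefit when alcohol does nothing

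*Combined protocol and SAP*

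**What the plan says.** Section 7.4.5 lists incident conditions, among them dementia, Class III or IV heart failure, breast cancer, serious liver disease or raised liver tests, eGFR below 30, organ transplant and a PHQ-9 score of 15 or more. It states that "the intervention will be discontinued at least temporarily in the following incident conditions". Its heading covers permanent and temporary stops and keeps these participants in follow-up for outcomes.

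Section 8.1.1 makes intention-to-treat the primary comparison. As secondary sensitivity analyses for non-adherence it adds, among others:

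- an as-treated analysis that "analyzes participants according to the amount of alcohol intake reported, regardless of what was assigned";
- a per-protocol rule, under which the "analysis excludes non-compliant participants from their respective arms".

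The section does not define non-compliance. It does not say whether intake is a fixed or time-varying exposure, whether non-compliant participants are censored or removed entirely, or how a 7.4.5 stop is treated. The same paragraph lists instrumental-variable, potential-outcomes and adherence-weighted log-rank analyses; the covariates for the weighting model are not named.

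**The concern.** An alcohol-arm participant who develops a listed illness stops drinking. An abstention-arm participant with the same illness has essentially nothing to stop and stays where they were. Grouping by reported intake then moves post-illness time and events from drinking to non-drinking. Removing or censoring the alcohol-arm stoppers takes illness out of one arm only. Because the primary endpoint includes death from any cause, these illnesses plausibly raise its rate, so the two groups stop being comparable for a reason unrelated to any effect of alcohol.

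These analyses are there to show what intention-to-treat may miss because of non-adherence. A spurious hazard ratio below 1 could be read as support for the main result, or as evidence that a null result was only dilution. The direction and size of the error also depend on choices the plan leaves open, so they should be fixed before the data are unmasked.

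**Working it through.** **1. The plan's own figure.** Section 8.2 asks for a "minimum of 80% power at a two-sided 0.05 significance level" with "a rate of 0.026/person-year" in the abstention arm, 1% annual loss, 10% non-adherence and a true hazard ratio of 0.82.

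- Effective hazard ratio: 0.9 × 0.82 + 0.1 × 1 = 0.838.
- Required events (Schoenfeld, 1:1): 4 × (1.960 + 0.842)² / (ln 0.838)² = 31.40 / 0.03124 = 1,005.1, so 1,006.
- Expected events with 3,900 per arm and follow-up uniform on 4.5-7.5 years: 1,009. Power is 80.2%.

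The 7,800 total reproduces, and the concern does not touch it.

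**2. Assumptions for the bias check.** The true hazard ratio is 1 and the overall event rate 0.026 per year. Both arms develop 7.4.5 conditions at rate s, and the event hazard is k times higher afterwards. Only the alcohol arm changes intake, permanently. The documents give neither s nor k; 1-3% per year and 2-3-fold are assumed. Other non-adherence and household clustering are left out.

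**3. Closed form over 6 years.** Let h be the event hazard while well, P0 the well person-time per participant and P1 the ill person-time, with f = P1/P0.

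- P0 = (1 − e^(−6(s+h))) / (s+h)
- P1 = [s / (s + h − kh)] × [(1 − e^(−6kh)) / (kh) − P0]
- As-treated, time-varying: drinking time is P0 from one arm; non-drinking time is P0 + 2P1. Rate ratio = (1 + 2f) / (1 + 2kf).
- Per protocol, alcohol arm censored at the stop: rate ratio = (1 + f) / (1 + kf).

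For s = 0.02 and k = 3, h = 0.0236 gives the overall rate of 0.026. Then P0 = 5.28, P1 = 0.288 and f = 0.0545.

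- As-treated: 1.109 / 1.327 = 0.836.
- Censored per protocol: 1.0545 / 1.1635 = 0.906.

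Across s = 1-3% and k = 2-3, the formulas give 0.949-0.779 and 0.973-0.867.

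**4. Simulation.** Cox hazard ratios from 1.5 million per arm, follow-up uniform on 4.5-7.5 years, 1% annual loss. Intention-to-treat gave 0.994-1.001 in these rows.

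| s per year | k | As-treated, time-varying | Per protocol, censored | As-treated, fixed | Per protocol, whole person excluded |
|---|---|---|---|---|---|
| 1% | 2 | 0.944 | 0.968 | 0.999 | 0.997 |
| 1% | 3 | 0.905 | 0.946 | 0.957 | 0.974 |
| 2% | 1.5 | 0.947 | 0.969 | 1.055 | 1.028 |
| 2% | 2 | 0.907 | 0.948 | 1.011 | 1.005 |
| 2% | 3 | 0.837 | 0.906 | 0.932 | 0.961 |
| 3% | 2 | 0.874 | 0.928 | 1.022 | 1.013 |
| 3% | 3 | 0.787 | 0.871 | 0.919 | 0.951 |

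The last two columns rise above 1 at small k because a participant must be event-free until the stop. Removing or reclassifying the whole person therefore takes event-free time out of the alcohol group.

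**5. False significant benefit.** From 1,000 simulated trials of 7,800, against a nominal 2.5% in that direction:

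| s, k | As-treated, time-varying | Per protocol, censored | As-treated, fixed | Per protocol, excluded |
|---|---|---|---|---|
| 1%, 3 | 37% | 12% | 9% | 5% |
| 2%, 3 | 83% | 34% | 21% | 9% |

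**6. Remedies under the same null.** Settings were s = 1% and 3% with k = 3, and s = 2% with k = 3 and 4. Counting the stop as adherent gives 0.998-1.005. Censoring both arms at the condition gives 0.999-1.007.

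**The case against.** The strongest reply is that the plan does not commit to the damaging versions. Non-compliance is undefined, and someone who stops because 7.4.5 requires it is following the protocol. The per-protocol wording most naturally removes whole persons, and the as-treated wording does not say intake is time-varying. This stands. A reader might infer that the plan excludes ordered stops, or that both analyses favour alcohol as written. The text supports neither: handling is unspecified, and the bias is near zero at a 2-fold hazard and reversed below it under whole-person exclusion or fixed reclassification. The reply does not remove the problem, since no exemption is written and a stopped participant meets the low-adherence trigger in Table 5.1.

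The size rests on assumed rates and on permanent stops, although 7.4.5 allows temporary ones, for example after raised liver tests or a high PHQ-9. This also stands.

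The adherence-weighted log-rank could correct for illness, but only if time-varying illness enters its model, which the plan does not say.

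Two further readings fail:

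- A reader might see a contradiction in the abstention arm. Section 5.2.2 says "Participants may consume a limited number of alcoholic beverages at their discretion on special occasions" while Section 5.1 says "those in the abstention arm will receive counseling if they fall below 100% adherence". But Section 5.4.3 refers to Table 5.1, which counts only drinking outside the vouchers. The 85% and 100% thresholds trigger counseling and are not analysis criteria. At most, 5.1 lacks a cross-reference to the table.
- Section 1.3.1 says "Some meta-analysts express concern about the possibility of inappropriate reference groups in many cohort studies", but does not describe those groups, so it cannot be cited as naming this mechanism.

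**Conclusion.** The concern holds for secondary sensitivity analyses. Section 7.4.5 changes intake in one arm in response to illness, and Section 8.1.1 has no rule for it. With permanent stops at 1-3% per year and a 2-3-fold event rate afterwards, a null effect would appear as about 0.95-0.78 in a time-varying as-treated analysis and 0.97-0.87 in a per-protocol analysis censored at the stop. Whole-person exclusion or fixed reclassification gives about 1.02-0.91. At 2% per year and 3-fold, the time-varying as-treated value of 0.84 is the same size as the design's effective hazard ratio of 0.838. That match depends on the assumed inputs and is not a forecast.

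A reader might infer that the main result or the sample size is compromised. Neither is: the primary comparison follows assignment, and the efficacy boundary in Section 8.1.3 uses the log-rank test on the primary and secondary endpoints. The defect should be corrected but does not threaten the trial's principal conclusion.

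**What to change.** In Section 8.1.1, leaving the clinical stopping rule as it is:

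1. Define non-compliance for the per-protocol set and count a stop ordered under 7.4.5 as compliance. The participant and all later events stay in the alcohol arm.
2. State whether as-treated intake is fixed or time-varying. Keep participants stopped under 7.4.5 in their pre-stop intake category, and label the analysis exploratory.
3. As a check only, censor both arms at the first 7.4.5 condition, limited to conditions ascertained equally in both arms: for example scheduled liver tests, PHQ-9, SAEs and the listed MACH15 AEs. Leave out eGFR, because Table 6.1 schedules creatinine at screening only. Dementia without hospitalization and heart-failure class are not listed AEs either, so it would be wrong to assume that every 7.4.5 condition is captured alike. Note that alcohol may itself affect some of these conditions (Sections 1.2.4 and 1.4.1), so this check is not free of bias.
4. Name these illnesses as time-varying covariates in the adherence model for the weighted log-rank test.

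Optionally, add a cross-reference from Section 5.1 to Table 5.1.

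The cost is SAP wording and one derived date per participant from data already scheduled. The downside is that the per-protocol estimate moves closer to intention-to-treat.
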